## 1.0 Background

Postoperative pain has significant short- and long-term implications for parturients undergoing cesarean delivery. Poorly controlled postoperative pain can interfere with the women's ability to care for herself and her newborn in the immediate postoperative period, and can contribute to longer length of hospitalizations . Untreated pain is associated with persistent pain, postpartum depression, and greater opioid use.

It is well established that an individualized, multimodal analgesic plan for the management of postoperative pain following cesarean delivery is associated with superior pain relief and decreased opioid consumption. While different institutional guidelines influence general practice patterns, a combination of several medications acting on different receptors has been shown to be effective in decreasing postoperative pain. In 2018, the cesarean section rate in the United States was 31.9%, compared to 20.7% in 1996. As the cesarean delivery rate increases, it is becoming more pertinent to develop and incorporate nonpharmacologic practices for postoperative pain.

The use of abdominal binders as an adjunct to pharmacologic therapy for the management of postoperative pain following major abdominal surgery has previously been discussed in surgical literature. Ossala et al (2020) published a recent meta-analysis of five randomized control trials evaluating the effectiveness of abdominal binders on postoperative pain following midline laparotomy. Their analysis showed significant reduction in postoperative pain on post-op days 1 and 5, though only one of the studies analyzes was from the United States, and the mean patient age was 61 years old.

The utility of abdominal support within the Obstetrics literature is both sparse and conflicting. Gillier et al (2016) published the first randomized control trial in the United States studying the use of abdominal binders following antepartum and intrapartum cesarean sections performed via Pfannenstiel incisions. In their study population of 155 women (87 binder vs 68 control), they found no difference in postoperative pain scores on postop days 1 and 2. Gustafson et al (2018) performed a similar, though smaller, study of 56 patients (29 binder vs 27 control), and did report statistically significant lower pain scores in the abdominal binder group ( $p= 0.019$ ). Of note, these two studies used different metrics to quantify postoperative pain. Neither of these two studies followed patients after hospital discharge, nor did they report on other postoperative complications including venous thromboembolisms or surgical site infections.

This paucity of evidence supporting or dissuading the use of postoperative abdominal support following cesarean section for the reduction of postoperative pain leaves important clinical questions unanswered. Additionally, there is an absence of long-term outcomes associated with the use of abdominal support devices. There remains a need for the development and implementation of nonpharmacologic methods for analgesia for women following cesarean sections, along with evidence-based recommendations regarding their use in postoperative patients. The ABBY (G-Squared Medical, Brentwood, TN) is an extended-wear panniculus retractor/tissue stabilizer that is intended for use postoperatively after abdominal procedure. It is placed directly onto patient skin, superior to a transverse incision, and is then used to elevate redundant tissues away from an incision or wound (<https://www.gsquareddmedical.com/How-it-Works.html>). The ABBY can be removed and replaced by patients and can be used for up to 10 days. This study aims to assess the effect of ABBY use on postoperative pain,

pain medication requirement, and patient satisfaction, when used as a patient-positioning device in women following cesarean delivery.

## **2.0 Rationale and Specific Aims**

**Primary Objective:** To compare the effects of post-operative patient positioning device, the ABBY, to standard wound dressings on postoperative pain in parturients delivered by cesarean delivery.

**Primary Outcome:** Postoperative opioid use post cesarean delivery

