## **4.0 Patient Population and Eligibility**

**Inclusion criteria:**

1. Age  $\geq$  18 years
2. Cesarean delivery
3. <36 hours post-delivery

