## **5.0 Enrollment/Randomization**

All residents and Labor and Delivery staff will be apprised of the study and appropriate patients with either planned cesarean delivery or those delivered by cesarean delivery within 36 hours will have the opportunity to participate in the trial. The research team will use a daily list of all cesarean deliveries in Epic to identify potentially eligible patients for enrollment. Prior to contacting the patient, the research team member will check with the patient's nurse or care team to discuss eligibility and appropriateness for the study. Notices will also be placed in Labor and Delivery regarding the study. Study personnel will explain the study to the patient and allow ample time for the subject to ask questions related to the study. If the subject consents, she will sign the informed consent document and will be provided with a copy of the consent form prior to randomization.

Patients will be enrolled either during their delivery admission up until 36 hours after delivery. After enrolling, randomization will be performed on the obstetric unit within the first 36 hours postpartum. Participants will be randomized in a 1:1 ratio using permuted blocks of 6. RedCap will be used for randomization, using an uploaded randomization sequence. A member of the study team will access RedCap to complete randomization. The randomization result will be noted with the patient's study number and retained in the research record.

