## **6.0 Study Procedures**

Methods: Patients who meet inclusion criteria and undergo cesarean delivery at Vanderbilt University Hospital center will be asked to participate. Informed consent will be obtained during the delivery admission. Enrolled patients will be randomized within the first 36 hours following cesarean delivery. The 36-hour window for randomization will begin at the completion of surgical case, as marked in the Anesthetic Care Record in the EMR.

Patients randomized to the treatment group will have the ABBY device applied by study personnel at the time of randomization, followed by continuation of usual postoperative care. The control group will have postoperative care per usual care.

Cesarean delivery will be performed by patients' surgical team, with surgical technique per surgeon preference. Women in the treatment group will have the ABBY device placed above the incision within 36 hours of cesarean delivery completion. All team members placing the ABBY device will undergo training and demonstrate competence.

Postoperative analgesia will be administered to all participants as per routine guidelines on postpartum. All study patients will receive an electronic survey at 10 days postoperatively and again at 14 days for those continuing to use the ABBY device or opioid medication at the 10-day survey.

Specific medical information regarding pregnancy and delivery will be collected and analyzed from the patients' electronic medical records.

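### The primary outcome as worded counts opioids taken before randomization, up to 36 hours the device cannot affect; no adjustment is planned, so the relative effect is diluted and some precision is lost, without bias

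*Combined protocol and SAP*

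**What the plan says.** Section 2.0 gives the primary outcome as "Postoperative opioid use post cesarean delivery". Delivery is the only anchor. No start or end of counting, unit or scale is stated.

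Patients may be approached before a planned cesarean, but allocation always comes after it:
- Section 4.0 sets eligibility at "<36 hours post-delivery".
- Section 5.0 says "randomization will be performed on the obstetric unit within the first 36 hours postpartum".
- Section 6.0 fixes the clock: "The 36-hour window for randomization will begin at the completion of surgical case".
- Section 6.0 also says that treated patients "will have the ABBY device applied by study personnel at the time of randomization".

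Both arms receive routine analgesia throughout.

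On follow-up, section 6.0 says "All study patients will receive an electronic survey at 10 days postoperatively". A second survey, on day 14, is sent only to women who reported at the first that they were still using the device or opioids. Section 1.0 adds that "The ABBY can be removed and replaced by patients and can be used for up to 10 days".

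Section 10.0 holds a sample-size statement (40% reduction in pain medication use, alpha 0.05, beta 0.20, 108 per group) and an accrual estimate. It gives no test, model or covariate, and no window for the 40%.

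**The concern.** Opioids given between the end of surgery and randomization cannot respond to a device that is not yet on. Under the section 2.0 wording they still enter the outcome, in an amount that depends on when each patient happened to be randomized. Two things follow. The relative effect shrinks, because part of the denominator is fixed before treatment starts. The comparison also carries extra between-patient variation, which a covariate could remove.

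The plan allows only 80% power, so it has little to spare. There is also an ambiguity of meaning: a 40% cut in total use since delivery asks more of the device than a 40% cut in use after placement, and section 10.0 does not say which is intended.

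**Working it through.** **Inputs from the documents.** 40% reduction, alpha 0.05, power 80%, 108 per group, 1:1 allocation (sections 5.0 and 10.0); randomization and placement at 0 to 36 hours after surgery (sections 5.0 and 6.0).

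**Assumptions, not in the documents.** Two-sided test; continuous cumulative dose; the same CV for use before randomization (X) and after it (Y); a 40% cut in Y only; correlation r between X and Y from 0 to 0.5.

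**The plan's own figure.** 108 cannot be reproduced, because no SD, control mean or control proportion is given. Back-solved by normal approximation, it needs CV = 0.4 / [√(2/108) × (1.960 + 0.842)] = 1.049. It also fits a control proportion of about 0.455–0.46 cut by 40%. With the noncentral t used below, 80% power at 108 per group needs a standardized difference d = 0.383, so CV = 0.4/0.383 = 1.044.

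**Share of use before randomization, f, at a constant rate of use.**
- 240-hour window (day 10): 18/240 = 7.5% at hour 18; 36/240 = 15% at hour 36.
- In-hospital window, length of stay assumed 72–96 hours: 18/96 = 19% to 18/72 = 25% at hour 18; 36/96 = 38% to 36/72 = 50% at hour 36.

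**Unadjusted total use, T = X + Y.** With the control mean of T set to 1:
- effect = 0.4 × (1 − f)
- SD = CV × √[f² + (1 − f)² + 2 r f (1 − f)]
- d = effect / SD

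Example, f = 0.25 and r = 0.5: effect = 0.30; SD = 1.044 × √0.8125 = 0.9415; d = 0.319; power 64.5%.

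| f | Apparent reduction | Power, r = 0 / 0.3 / 0.5 | n per group for 80%, r = 0 to 0.5 |
|---|---|---|---|
| 0.075 | 37% | 79.7 / 77.9 / 76.6% | 109–118 |
| 0.15 | 34% | 78.8 / 74.8 / 72.2% | 112–131 |
| 0.25 | 30% | 75.7 / 68.7 / 64.5% | 120–156 |

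**Counting from randomization, unadjusted.** 80% for any f, by construction of the CV.

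**Adjusting for X.** Because T = X + Y, a linear model of T on arm and X has the same arm coefficient and standard error as a linear model of Y on arm and X. A simulated data set confirmed this (estimate −0.1762, SE 0.0700 for both outcomes). The standardized difference becomes 0.383/√(1 − r²). With one degree of freedom lost, power is 80.0 / 83.6 / 89.9% at r = 0 / 0.3 / 0.5, whichever of T or Y is the outcome.

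**If the 40% means total use.** Later use must fall by 0.4/(1 − f): 43%, 47% and 53% at f = 0.075, 0.15 and 0.25.

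**Check with unequal randomization times.** 6,000 simulated trials per setting, randomization uniform over 0–36 hours, gamma-distributed use, CV about 1.3 so that unadjusted post-randomization use has 79–83% power, r 0.06–0.33. Unadjusted total use had 77–81% power for a 240-hour window at constant rate, 60–69% for 72 hours, and 63–72% for 240 hours with use halving every 48 hours (mean f 0.23). Adjusting for earlier use and hours to randomization gave 82–86% in every setting. Hours alone recovered nothing, so earlier use is the covariate that matters.

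**If the outcome were binary (any use since delivery).** A patient who used opioids before randomization is already a yes. Take a control proportion of 0.455 and a 40% cut among later-only users. If a quarter of control users had already used, the treated proportion is 0.455 × (0.25 + 0.75 × 0.6) = 0.3185 and power is about 54%. If half had, it is 0.455 × (0.5 + 0.5 × 0.6) = 0.364 and power is about 27%.

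**The case against.** The strongest reply is that section 2.0 does not state a start time at all. Its wording may describe the setting rather than the moment counting begins, and no adjustment is planned only because no analysis is described. That is fair. The firm fact is an undefined window; counting from delivery is the plain reading, not an explicit rule. But a team filling the gap could easily choose total use since delivery, unadjusted, and nothing in the documents steers it away from that. If use after discharge was intended, the point falls away, but no text says so.

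Second, the loss may be small. The follow-up that the documents describe runs to day 10. At constant use over that window, unadjusted power stays at 77–80% for randomization at hour 18, and at 72–79% even if every patient is randomized at hour 36. Thirty-six hours is a maximum, and patients who consent before a planned cesarean could be randomized soon after it. This stands, and it limits the claim.

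Third, total opioid consumption since delivery is a legitimate quantity to report. That also stands. It is a reason to keep it as a secondary outcome and, if it remains primary, to adjust it.

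A reader might infer that the treatment comparison is biased. It is not: use before randomization is balanced in expectation, and the absolute difference is unchanged. A reader might also infer that a binary outcome would avoid the problem. For any use since delivery the opposite holds, as the working shows.

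**Conclusion.** The point holds as an inexpensive improvement. As worded, the outcome takes in use that the device cannot affect, and no adjustment is planned. The result is a relative effect diluted to 40% × (1 − f) and some loss of precision.

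The size is conditional on f, r, the CV, the scale and the window, none of which the documents give. Under the stated assumptions the loss is 0 to 3 percentage points of power at f = 0.075 and 1 to 8 at f = 0.15. Power of 65–76% needs f = 0.25, which means a short in-hospital window or use concentrated early. Reading the point as a major loss of power is not supported: power near 37–51% needs f = 0.50, for example every patient randomized at hour 36 of an assumed 72-hour stay.

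Nor does adjustment alone settle everything. The equality between total and post-randomization use is exact only for the absolute difference in a linear model on the raw scale. In simulations on log and rank scales the match was close, but power for total use was up to about 3.5 points lower. On any scale, a percentage of total use remains diluted unless counting starts at randomization.

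**What to change.** 1. Adjust the primary comparison for opioid use from the end of surgery to randomization. This recovers the precision in a raw-scale linear model whichever outcome is kept, and costs one degree of freedom.
2. Count the primary outcome, for example in morphine milligram equivalents, from randomization to a fixed end point common to both arms, with total use since delivery as secondary. The percent reduction then refers to use the device can affect. If the end point is fixed relative to surgery, windows differ by up to 36 hours between patients; include hours from surgery to randomization as a covariate for that purpose only.
3. State in section 10.0 which window the 40% refers to.
4. If the intended outcome is binary (any use), count only use after randomization or after discharge. If it is use after discharge on any scale, say so in section 2.0.

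Cost: the covariate needs only in-hospital doses, since randomization takes place on the obstetric unit, but record abstraction must split doses at the randomization time, and section 6.0 does not list dose data among the items collected. An end point after discharge would need a survey question on opioid quantity, which relies on recall and is not shown to be in the survey; total use carries the same cost. Day 10 is the last time at which every patient is asked, because the day-14 survey goes only to those still using the device or opioids.

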**Secondary Objectives:**

- To evaluate subjective pain scores, patient satisfaction, and duration of use of patient positioning device.
- To evaluate surgical complication and costs in groups with and without patient positioning device

## **3.0 Animal Studies and Previous Human Studies**

The utility of abdominal support within the Obstetrics literature is both sparse and conflicting. Gillier et al (2016) published the first randomized control trial in the United States studying the use of abdominal binders following antepartum and intrapartum cesarean sections performed via Pfannenstiel incisions. In their study population of 155 women (87 binder vs 68 control), they found no difference in postoperative pain scores on postop days 1 and 2. Gustafson et al (2018) performed a similar, though smaller, study of 56 patients (29 binder vs 27 control) and did report statistically significant lower pain scores in the abdominal binder group (p= 0.019). Of note, these two studies used different metrics to quantify postoperative pain. Neither of these two studies followed patients after hospital discharge, nor did they report on other postoperative complications including venous thromboembolisms or surgical site infections.

## **4.0 Patient Population and Eligibility**

**Inclusion criteria:**

1. Age  $\geq$  18 years
2. Cesarean delivery
3. <36 hours post-delivery

**Exclusion criteria:**

1. Vertical skin incision
2. Inability to place device superior to incision
3. Presence of surgical drain
4. Opioid use disorder
5. Chronic opioid use ( $\geq$  14 consecutive days during pregnancy)
6. Allergy to device adhesive
7. Active COVID-19 infection
8. Patient unable to consent

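### Device placeability is an exclusion criterion, yet the only placement described comes at randomization and in the ABBY arm alone, with no fit check in all women beforehand and no rule for failed placement

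*Combined protocol and SAP*

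**What the plan says.** All references are to the combined protocol and SAP.

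- Section 4.0, exclusion 2 of 8, reads "Inability to place device superior to incision". It names no assessor, method or time.
- Section 5.0 identifies candidates from a daily Epic list of cesarean deliveries. It then says: "Prior to contacting the patient, the research team member will check with the patient's nurse or care team to discuss eligibility". The trial is offered to "appropriate patients with either planned cesarean delivery or those delivered by cesarean delivery within 36 hours", so some women may be approached before there is an incision. On timing: "After enrolling, randomization will be performed on the obstetric unit within the first 36 hours postpartum".
- Section 6.0 says: "Patients randomized to the treatment group will have the ABBY device applied by study personnel at the time of randomization". It adds: "All team members placing the ABBY device will undergo training and demonstrate competence". For the other arm: "The control group will have postoperative care per usual care".
- Section 9.0 covers withdrawal at the patient's own wish only. It does not deal with failed placement.
- Section 10.0 gives a sample size and a recruitment estimate. It defines no analysis population, does not say that women are analysed as randomized, and has no rule for an allocated woman in whom the device cannot be placed.

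**The concern.** An entry criterion protects the comparison only if it is judged in the same way in both arms, before allocation is known. Here the one step that directly tests placeability takes place in one arm and at allocation. If placement fails, the woman meets a listed exclusion, and staff have a protocol-based reason to call her ineligible. A control woman with the same abdomen and incision is never tested and stays in.

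Placeability depends on anatomy and wound, which could plausibly relate to pain, opioid use and complications, and these are the trial's outcomes. If such women were removed from ABBY alone, the arms would no longer be comparable, and a larger sample would not repair that. If they are kept instead, they dilute the device effect. A fit check before allocation reduces both problems.

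**Working it through.** **Step 1. The sequence as documented.**

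| Step | Who is assessed | Is device fit examined? |
|---|---|---|
| Epic list (5.0) | All cesarean deliveries | No |
| Care-team discussion before contact (5.0) | All candidates | Not described; it is a conversation |
| Consent (5.0, 6.0) | All who agree; may precede surgery if planned | Not described |
| REDCap allocation (5.0) | All consented | Not described |
| Placement by trained staff (6.0) | ABBY arm only | Yes, in effect |

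The criterion is therefore directly tested in one arm only.

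**Step 2. The plan's own figure.** Section 10.0 gives 108 per group for a 40% reduction at alpha 0.05 and beta 0.20, with no SD, baseline mean or baseline rate. The figure can only be back-solved. For two means, two-sided, n = 2(1.960 + 0.842)² × (CV/0.4)², and n = 108 implies CV ≈ 1.049 (CV 1.04 gives 107, CV 1.05 gives 109). A comparison of proportions with a control rate of about 0.46 gives 107, so it fits about as well. The figure can be neither confirmed nor called wrong, and the point does not depend on it. The CV of 1.049 is used below for illustration only.

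**Step 3. Effect of one-arm removal when the device does nothing.** Assumptions, none of them in the documents: a share p of the ABBY arm cannot have the device placed, and their mean opioid use is r times that of the other women.

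Spurious reduction in the ABBY mean = 1 − 1/(1 − p + p·r)

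| p (women of 108) | r = 1.25 | r = 1.5 | r = 2 |
|---|---|---|---|
| 3% (about 3) | 1 − 1/1.0075 = 0.7% | 1 − 1/1.015 = 1.5% | 1 − 1/1.03 = 2.9% |
| 5% (about 5) | 1 − 1/1.0125 = 1.2% | 1 − 1/1.025 = 2.4% | 1 − 1/1.05 = 4.8% |
| 10% (about 11) | 1 − 1/1.025 = 2.4% | 1 − 1/1.05 = 4.8% | 1 − 1/1.10 = 9.1% |

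If r were below 1, the shift would go the other way.

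**Step 4. Type I error.** Normal approximation, CV 1.049, SE = 1.049 × √(1/108 + 1/n₂), where n₂ is the number left in the ABBY arm.

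- p = 5%, n₂ = 103: two-sided error 0.051 (r = 1.25) to 0.063 (r = 2).
- p = 10%, n₂ = 97: 0.053 (r = 1.25) to 0.095 (r = 2).

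**Step 5. Cost of keeping every woman as randomized.** If those without the device get no benefit, the average effect is 0.4 × (1 − p). With 108 per group, power falls from 0.80 to 0.76 at p = 5% (effect 0.38) and to 0.71 at p = 10% (effect 0.36). Finding such women before allocation avoids most of this loss.

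**The case against.** The strongest reply is that this is an ordinary entry criterion, listed beside vertical incision and drain, and that entry criteria are normally applied before allocation. Inclusion 3 requires a woman to be less than 36 hours post-delivery, so eligibility cannot be complete before surgery, and the incision exists whenever allocation is made. The Epic list is a post-delivery source. The care team consulted after delivery can know the incision and wound, and study personnel meet the woman before consent. Vertical incisions and drains are already excluded in both arms, so frequent failure among the remaining women is not shown. A general statement that women are analysed as randomized would remove the bias by itself.

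Much of this stands. Obvious cases may well be screened out of both arms. But the step described is to "check with the patient's nurse or care team to discuss eligibility and appropriateness for the study", which is not a documented judgement of fit by someone trained on the device, and no recheck between early consent and allocation is described. An as-randomized rule would prevent the bias but leave the dilution, which the pre-allocation check reduces.

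A reader might also infer that the protocol drops ABBY women whose placement fails, or that the resulting bias favours the device. The documents support neither. They are silent on what happens after failed placement, and nothing in them links unplaceability to opioid use in either direction.

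**Conclusion.** The point holds as an unguarded risk. It is not a stated procedure of one-arm exclusion. The criterion is directly tested only at randomization and only in the ABBY arm, the earlier steps include no fit check in all women, and section 10.0 does not fix the analysis set.

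The 0.7% to 9.1% range in the ABBY mean rests wholly on the assumed failure rates and relative opioid use, with removal assumed to occur. The middle case, 5% failure with 50% higher use, gives 2.4%, which is small beside the 40% target. The type I error approaches 0.10 only when 10% of placements fail and those women use twice the opioid. The case for acting is that the remedy is cheap and reduces both bias and dilution, not that a large distortion has been shown.

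**What to change.** In sections 5.0 and 6.0, require a device-trained team member to confirm, after surgery and immediately before the REDCap allocation is opened, that the device could be placed above the incision. Do this in every consented woman, recheck incision type and drain at the same moment, and record the result in one REDCap field.

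In section 10.0, state that every allocated woman is analysed in her assigned arm for all outcomes even if placement then fails, and that failed placement is reported as a device outcome.

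The cost is a brief bedside look by staff who are trained already, one data field and one analysis sentence. The few failures that still occur after allocation will slightly dilute the ABBY effect.
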